Study Protocol and Statistical Analysis Plan

Study Title:
TeamTRACS Pilot (CTSI)

ClinicalTrials.gov ID (NCT number):
NCT05370157

Document Date:
March 14, 2024

Study Overview

This research study is a cluster-randomized controlled effectiveness-implementation hybrid trial of TeamTRACS. The trial will take place in 6 rural Child Advocacy Centers (CACs) in the southern United States. It will use mixed methods (quantitative and qualitative) to evaluate the effects of TeamTRACS and assess the acceptability, appropriateness, and feasibility of self-guided implementation via pre/post surveys and qualitative interviews.

The primary aims of this pilot trial are to test the effects of TeamTRACS on knowledge, skill use, and team functioning in addition to evaluating the acceptability, appropriateness, and feasibility of self-guided implementation. Six rural CACs will be randomized to TeamTRACS ($n = 4$ CACs) or a waitlist comparison ($n = 2$ CACs). Participants will be team members at participating CACs (estimated $N = 25$ per CAC; total $N = 150$). We expect team members to change during the study period and will include only current team members at each timepoint. We will evaluate the effects of TeamTRACS on learning (i.e., knowledge), transfer (i.e., skill use), and results (i.e., team functioning). Knowledge, skill use, and team functioning will be assessed at baseline and 3 months with online surveys and qualitative interviews of team members. We will also assess hypothesized long-term outcomes (i.e., team performance, workforce outcomes). Individuals involved in implementation in the 4 CACs randomized to TeamTRACS will participate in semi-structured key informant interviews during the implementation process. They will rate the acceptability, appropriateness, and feasibility of self-guided implementation at the beginning, middle, and end of the study, and we will track completion of implementation activities in each CAC.

Background

Children in rural areas are nearly twice as likely as their urban peers to experience maltreatment, increasing risk for physical/mental health, academic/vocational, and interpersonal problems. They have high rates of unmet mental health needs and experience greater impairment than those in urban areas. CACs are uniquely suited to serve at-risk rural children through effective, efficient, and trauma-informed investigations and services. Rural Child Advocacy Centers (CACs) rely on multidisciplinary team members employed by independent organizations.

Interventions that improve team functioning can improve teams' performance, strengthen the workforce, and ultimately improve service quality and outcomes for children and families. Team training is a specific type of team intervention that targets affective, behavioral, and cognitive team functioning by teaching teamwork knowledge, skills, and abilities. We recently adapted TeamSTEPPS to fit CAC multidisciplinary teams. TeamSTEPPS, developed by the Agency for Healthcare Research and Quality, is the most widely used model of team training in healthcare and a promising model for improving team functioning in other service settings. We worked collaboratively with CAC team members and leadership to adapt the format (in-person to virtual), setting/population (healthcare to CACs), personnel (internal trainer to external trainer), and content (e.g., tailoring language, reordering). Our adapted training, TeamTRACS (**T**eam **T**raining in **R**oles, **A**wareness, **C**ommunication, and **S**upport), is designed to fit the specific needs and context of CAC multidisciplinary teams. It targets knowledge, skills, and attitudes related to team member roles, shared awareness, communication, mutual support, and goal-setting. TeamTRACS is structured, easy to use, flexible in length and intensity, and requires few

resources. We piloted TeamTRACS with one rural CAC and found high acceptability, appropriateness, and feasibility (ratings >4 on 1-5 scale).

This research study will test the effectiveness of TeamTRACS in a cluster-randomized trial in 6 rural Child Advocacy Centers. We will also partner with the National Child Advocacy Center (NCAC) to refine our implementation strategies. Rural teams serving high-need/low-resource areas may find it challenging to implement new practices. This study will use a self-guided implementation approach that requires few resources and builds local capacity for change. We will assess the acceptability, appropriateness, and feasibility of self-guided implementation in participating CACs. Self-guided implementation will allow the training to be rapidly scaled up and disseminated to CACs nationwide. Improving teamwork in CACs has the potential to positively impact service quality and outcomes for hundreds of thousands of children served by CACs.

Procedures

Randomization

CACs will be randomized to TeamTRACS ($n = 4$) or a waitlist comparison ($n = 2$) using an online randomization tool. We may stratify CACs based on team size if there is significant variability across the 6 CACs. CACs randomized to TeamTRACS will receive the intervention described below after completing the baseline survey. CACs randomized to the waitlist will receive the intervention after completing the follow-up survey.

Team Training Intervention

TeamTRACS (**T**eam **T**raining in **R**oles, **A**wareness, **C**ommunication, and **S**upport), is a team training intervention that is adapted from TeamSTEPPS (Team Strategies and Tools to Enhance Performance and Patient Safety), which is a widely used evidence-based team training approach developed by the Agency for Healthcare Research and Quality. TeamTRACS was developed via a systematic and participatory adaptation process (see McGuier et al., 2023).

TeamTRACS targets knowledge, skills, and attitudes related to team member roles, shared awareness, communication, mutual support, and goal-setting. TeamTRACS is structured, easy to use, flexible in length and intensity, and requires few resources. It incorporates didactic instruction, discussion, and interactive activities and can be delivered virtually or in-person. Presentation slides, detailed instructor guides, and worksheets were created for each module (see “TeamTRACS Instructor Guide”). Team members are encouraged to identify specific goals for their team and make plans to use specific strategies from the training. The training will be delivered in a single session and be at least 4 hours. Teams will determine the length and delivery method (e.g., in-person vs. virtual) as part of the implementation process. The training workshop will be facilitated by an experienced team trainer from NCAC; this approach is responsive to pilot data favoring use of an external facilitator and is sustainable given available resources.

All team members at each CAC will be invited to participate in the training. Prior to the start of the training, the PI will review a brief consent script and provide an opportunity for questions. A copy of the consent script will be provided to all team members. We will record team members’ attendance at the training.

Baseline and Follow-up Surveys

Team members will complete online surveys (<30 minutes) before training and 3 months after training via REDCap, a secure online database. The surveys will assess knowledge and use of teamwork skills, team functioning, team performance, and team member work outcomes (see “Team Member Survey”). Team members will be sent an email with information about the study and a link to review the online consent form.

Key Informant Interviews

In the 4 CACs randomized to TeamTRACS, key informants (leadership and team members involved in the implementation process) will be invited to participate in qualitative interviews. Semi-structured interviews will be conducted approximately once a month during the implementation process to assess change over time. Questions will assess perceptions of and experiences with self-guided implementation, as well as progress through implementation phases and steps (see “Implementation Interview Guide”). Interviews will take 30-60 minutes. Key informants will also rate the acceptability, appropriateness, and feasibility of self-guided implementation at the beginning, middle, and end of the study.

Document Collection

CAC staff at the 4 CACs randomized to TeamTRACS will be asked to share documents created during the implementation process, including completed worksheets, action plans for training, team goals, and revised policies or protocols. The research team will review documents to assess fidelity to the implementation guide and completion of implementation activities. At all 6 CACs, staff will be asked to report team members’ attendance at case review meetings and any changes in team members (e.g., turnover, addition of new members).

Statistical Analysis Plan

Preparatory Analyses

We will calculate survey response rates, look for patterns of missing data, and examine descriptive statistics for all measures.

Analyses of Effectiveness Outcomes

We will test changes in knowledge, skill use, and team functioning from baseline to 3-month follow-up using linear mixed models to account for repeated measures and clustering within CACs. We will also explore changes in team performance and team member outcomes. Our primary analyses are intent-to-treat analyses including all participants in each condition. We will also conduct ‘per protocol’ analyses testing for changes in knowledge and skill use by training attendance. This pilot study is adequately powered to detect changes in individual outcomes (e.g., knowledge of teamwork skills), but underpowered for team-level outcomes. Accordingly, after aggregating measures of team functioning and performance to the team level (assuming sufficient within-team agreement), we will plot data to visually examine team-level results.

Analyses of Implementation Outcomes

We will use rapid analysis to code qualitative key informant interviews using an a priori coding scheme focused on barriers, facilitators, and suggestions for change. We will assess the proportion of implementation activities completed in each CAC and examine descriptive

statistics for acceptability, appropriateness, and feasibility ratings. Mean ratings >4 on the 1-5 scale will indicate that TeamTRACS is acceptable, appropriate, and feasible.

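### Does counting people who join after the single training session undermine the primary analysis of knowledge and skill use?

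*Combined protocol and SAP*

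**What the plan says.** The Study Overview foresees turnover and sets a rule for it: "We expect team members to change during the study period and will include only current team members at each timepoint". Six CACs are randomized, four to TeamTRACS and two to waitlist, with about 25 members each.

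Under Procedures, Team Training Intervention: "The training will be delivered in a single session and be at least 4 hours". Also: "All team members at each CAC will be invited to participate in the training". No later session for new members of a trained team is described. Attendance is recorded. Under Baseline and Follow-up Surveys: "Team members will complete online surveys (<30 minutes) before training and 3 months after training via REDCap". Under Document Collection, staff at all six CACs report turnover and new members.

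The Statistical Analysis Plan, Analyses of Effectiveness Outcomes, states: "We will test changes in knowledge, skill use, and team functioning from baseline to 3-month follow-up using linear mixed models". It adds: "Our primary analyses are intent-to-treat analyses including all participants in each condition". A secondary per-protocol analysis is described as "analyses testing for changes in knowledge and skill use by training attendance".

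**The concern.** Learning and transfer happen within a person. Someone hired after the session has no baseline survey and could not have been taught directly, yet answers the follow-up survey as a TeamTRACS participant. The estimated change then mixes learning with turnover and, if joiners gain nothing, is pulled towards zero. The plan does not say whether its target is learning among members present at the start or knowledge in the team as it stands at 3 months. Nor does it say how a person without a baseline enters a model of change. The per-protocol analysis does not settle this: it is a non-randomized comparison and puts joiners together with members who missed the session. If the dilution were large, the trial could understate its effect on the very outcomes for which it claims adequate power.

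**Working it through.** **What the plan implies.** Current members at each survey (Study Overview), combined with all participants in each condition (Statistical Analysis Plan), place a joiner in the arm of the joiner's CAC. Inclusion is therefore implied. The target effect and the treatment of a missing baseline are not stated.

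**Plan's own figure.** 6 × 25 = 150, split 4 × 25 = 100 and 2 × 25 = 50. This reproduces. The statement on power has no inputs and cannot be reproduced.

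**Share of joiners (assumed; no rate in the documents).** Only people who join in the 3 months between training and follow-up matter. With annual turnover *t*, the share is f = 1 − (1 − t)^(3/12).
- t = 20%: f = 1 − 0.80^0.25 = 0.054
- t = 40%: f = 1 − 0.60^0.25 = 0.120

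**Dilution if joiners gain nothing.** An unpaired comparison keeps 1 − f of the effect, that is 0.946 or 0.880. The planned mixed model loses less, because members with both surveys carry more of the information about change. For two waves, each leaver replaced by one joiner, and within-person correlation ρ (clustering left aside), the share kept is (1 − f)/(1 − fρ).

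| f | ρ | Share kept | Estimate if the true effect is 0.50 SD |
|---|---|---|---|
| 0.054 | 0.4 | 0.946/0.978 = 0.967 | 0.48 |
| 0.054 | 0.7 | 0.946/0.962 = 0.983 | 0.49 |
| 0.120 | 0.4 | 0.880/0.952 = 0.924 | 0.46 |
| 0.120 | 0.7 | 0.880/0.916 = 0.961 | 0.48 |

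**Fuller check.** Generalized least squares for 4 against 2 CACs of 25, with assumed ICC 0.02 or 0.10 (between-wave CAC correlation 0.8), ρ 0.4 or 0.7, response 100% or 60%, and both values of f: 16 settings.
- Current members: 0.479–0.491 at f = 0.054 and 0.452–0.480 at f = 0.120. Baseline roster: 0.500.
- Standard error of the current-member estimate: about 0.16–0.31 SD. The shift of 0.01–0.05 SD is 0.04–0.18 of one standard error.
- Standard error of the baseline-roster estimate: 0.2–2.4% larger. Effect divided by standard error: 1–8% lower for current members.
- Root mean squared error around 0.50: equal (to rounding) or lower for current members in all 16 settings.

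**What that check leaves out.** It has no gap between baseline and training. In the plan, training follows the baseline survey after an implementation process in which key informants are interviewed about monthly. People who join in that gap are invited and can be trained, yet a baseline-roster rule drops them.
- Assumed 3-month gap at 40% turnover (12% trained joiners): the standard-error penalty of the baseline roster rises to about 5%, and the effect/SE disadvantage of current members narrows to 1–6% over the turnover range.
- Assumed 6-month gap: 1 − 0.60^0.5 = 0.225 trained joiners, a penalty of roughly 8–9%, and a disadvantage of 1–4%.

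**The case for a change.** The strongest case for a change is that knowledge and skill use are individual outcomes, that follow-up membership arises after randomization and could itself be affected by the intervention, and that the baseline roster could not. Two analysts might read the plan differently and report different primary estimates. In the fuller check the effect/SE ratio favored the baseline roster in every setting. Heavier turnover would hurt more: from a starting power of 80%, unpaired dilution gives 71% at 10% joiners and 61% at 20%.

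Part of this stands. The target effect is not written down, and dilution is real if joiners learn nothing from trained colleagues. The rest weakens on inspection:
- The direction in every setting largely follows from giving each joiner zero effect. Any spillover shrinks the gap.
- The power figures are for an unpaired analysis. With the planned model, ρ = 0.5 and 10% joiners, the share kept is 0.90/0.95 = 0.947. The noncentrality falls from 2.802 to 2.802 × 0.947 = 2.653, and power is Φ(2.653 − 1.960) = 0.756, rather than 71%.
- Twenty percent joiners within 3 months corresponds to annual turnover of 1 − 0.80^4 = 59%.
- A baseline cutoff does not match the complaint, which concerns joining after training. A present-at-training cutoff needs an invented date in waitlist CACs, which train only after follow-up.
- Neither rule cures selection through leavers.

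**Conclusion.** The concern does not call for a change. Keeping current members is a stated choice that suits a trial randomizing whole teams in an effectiveness-implementation design. On that target, the smaller effect in recent joiners belongs to the effect being estimated and is not a bias. If learning among original members is the target instead, the estimate is low by about 0.01–0.05 SD out of 0.50, under 0.2 of a standard error. That size rests on assumed turnover of 20–40% a year, no spillover, and the assumed ICC, correlations and response rates above. None of these is in the documents.

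A baseline-roster primary would buy this small gain by excluding trainable joiners and accepting a wider standard error. Reasonable statisticians would differ on it, so it is a fair trade-off. The unstated handling of a missing baseline is a gap that the method fills: a linear mixed model uses a person with one survey, whether leaver or joiner. Recorded attendance, reported turnover and the by-attendance analysis let the analysts describe joiners and leavers by arm. They can also rerun the model on members present at baseline as an ordinary sensitivity check, without altering the primary analysis.

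### The SAP's mixed model names no CAC-by-time term and no small-sample degrees of freedom, so with 4 versus 2 CACs the usual random-intercept version can understate uncertainty

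*Combined protocol and SAP*

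**What the plan says.** The Randomization section states: "CACs will be randomized to TeamTRACS ($n = 4$) or a waitlist comparison ($n = 2$) using an online randomization tool". The Study Overview expects about 25 team members per CAC, 150 in all, surveyed at baseline and 3 months. It foresees turnover: "We expect team members to change during the study period and will include only current team members at each timepoint".

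The model is given in one sentence of the SAP, under Analyses of Effectiveness Outcomes: "We will test changes in knowledge, skill use, and team functioning from baseline to 3-month follow-up using linear mixed models". The sentence describes the method as "using linear mixed models to account for repeated measures and clustering within CACs". The same paragraph adds "Our primary analyses are intent-to-treat analyses including all participants in each condition" and "This pilot study is adequately powered to detect changes in individual outcomes". It calls the study underpowered for team-level outcomes, which will be plotted.

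The documents do not list the random effects, the degrees of freedom, an ICC, an effect size or an alpha level.

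**The concern.** Six CACs are randomized, so the uncertainty of the treatment effect depends on how much CACs differ in their change over 3 months. A person intercept deals with repeated measures and a CAC intercept deals with clustering, so a model with only those two terms meets the SAP sentence. Neither term describes a CAC whose members all move up or down together between the surveys.

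If such shifts occur, the intercept-only model treats 150 people as if they had been randomized individually. A local event at one of only two waitlist CACs could then be read as a training effect. Adding a CAC-by-time term does not settle the matter if the result is judged against a normal distribution, because its variance is estimated from six CACs.

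**Working it through.** **Inputs from the documents.** 6 CACs, 4 versus 2; about 25 members each; two survey waves. The headcount reproduces: 6 × 25 = 150, or 100 versus 50 by arm. The power statement cannot be reproduced, because no effect size, SD, ICC or alpha is given.

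**Assumptions.** Two-sided 5% level. A member's change is d = arm effect + u + e, where u is shared by the CAC. Total variance is 1 and Var(u) = ICC, taken as 0 to 0.10. There are 25 complete pairs per CAC unless stated otherwise.

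**Step 1: what the intercepts do.** With complete pairs, person and CAC intercepts both subtract out of d, but u does not. The model's variance for the arm contrast is about 1/100 + 1/50 = 0.03. The true variance is 0.03 × (1 + 24 × ICC).

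**Step 2: error of the intercept-only test.** Error = 2Φ(−1.96/√(1 + 24 × ICC)). At ICC 0.05, √2.20 = 1.483 and 1.96/1.483 = 1.32, which gives 18.6%. Simulation (400,000 runs) agrees within about 1 point. Fitting the mixed model itself to 200 data sets per setting rejected 6.5% at ICC 0 and 21.5% at 0.05; a t test on individual changes in the same data rejected 6.0% and 21.0%. A separate 150 data sets gave 10.7% and 19.3% for the mixed model, and the change-score t test gave the same. These runs are too small to fix a rate, but they show that the two analyses agree.

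**Step 3: the alternatives.** The CAC-by-time rows use REML with the variance truncated at zero. It was estimated as zero in 59%, 47%, 38%, 22% and 10% of runs, in ICC order. The CAC-mean test compares six mean changes with t on 4 df (critical value 2.776).

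| Assumed change ICC | 0 | 0.01 | 0.02 | 0.05 | 0.10 |
|---|---|---|---|---|---|
| 1 + 24 × ICC | 1.00 | 1.24 | 1.48 | 2.20 | 3.40 |
| Error %, person and CAC intercepts, 25 pairs | 5.0 | 7.8 | 10.7 | 18.6 | 28.8 |
| Error %, same, 15 pairs | 5.0 | 6.6 | 8.3 | 13.3 | 20.6 |
| Error %, CAC-by-time, Wald z | 3.9 | 5.6 | 6.7 | 9.2 | 10.9 |
| Error %, CAC-by-time, 4 df always | 0.4 | 0.9 | 1.3 | 2.5 | 3.7 |
| Error %, CAC-by-time, 4 df, but 148 df at zero variance | 3.0 | 4.0 | 4.4 | 5.3 | 5.3 |
| Error %, CAC-mean t, 4 df | 5.0 | 5.0 | 5.0 | 5.0 | 5.0 |
| Power % at 0.5 SD, CAC-mean t | 59 | 50 | 44 | 32 | 23 |
| 95% CI half-width in SD, CAC-mean t | 0.48 | 0.54 | 0.59 | 0.71 | 0.89 |

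The last two rows use SE = √(0.75 × (ICC + (1 − ICC)/25)) and a noncentral t on 4 df. At ICC 0, SE = √0.03 = 0.173 and 2.776 × 0.173 = 0.48. The individual-level comparison at ICC 0 has power 82% and half-width 1.96 × 0.173 = 0.34.

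**Step 4: turnover.** Assume that 15 of 25 respondents per wave are paired, with variances of 0.05 (CAC), 0.45 (person) and 0.50 (residual). The intercept-only error is then 5.0%, 7.3%, 9.6%, 16.3% and 25.3% over the same ICCs. The CAC-mean t stays at 5.0–5.1%.

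**Step 5: where the CAC-mean t fails.** The table assumes equal team sizes and the same between-CAC variance in both arms.
- If only the waitlist CACs vary in change, error is about 8% (waitlist ICC 0.05) or 11% (0.10). If only the trained CACs vary, it is 3.4% or 2.9%.
- With assumed team sizes of 10, 15, 20, 30, 35 and 40, error averages 4.8–5.0% over the 15 possible allocations. With both smallest teams on the waitlist at ICC 0 it is 8.5%.

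**The case against.** The strongest defence is that the SAP promises to handle clustering, and a competent analyst could meet that promise with a sound model. Harm needs two conditions: the intercept-only reading is chosen, and CACs do differ in change. The documents establish neither. A reader might infer that the trial's error rate is 19% or 29%. The documents do not support that; those figures illustrate assumed ICCs of 0.05 and 0.10.

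A reader might also cite the Team Training Intervention section, where teams choose training length and format, as proof that CACs will differ in change. It is weak support for an inflated error rate. Those choices arise only in trained CACs, and if training has no effect they create no differences.

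Nor should one infer that no between-arm comparison is planned. The controlled design and the intent-to-treat sentence imply one.

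The pilot status carries some weight, and it argues for estimates with intervals over significance tests. It does not dispose of the point. The low-power caveat covers team-level outcomes only, whereas individual outcomes are called adequately powered and their treatment contrast rests on the same six CACs.

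It stands that the planned mixed model need not be replaced. With a CAC-by-time term and a fixed rule for a zero variance estimate it holds 3.0–5.3% under the common-ICC assumptions above.

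**Conclusion.** The point holds as an omission with a conditional consequence. The text does not exclude the usual random-intercept model, whose standard error for change ignores CAC differences in change. With 25 complete pairs per CAC, its true standard error exceeds the reported one by a factor of 1.11 at ICC 0.01 (√1.24) and 1.48 at ICC 0.05 (√2.20). At ICC 0 there is no inflation, and the actual ICC is unknown.

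Two stronger conclusions are not supported. The planned model cannot be called invalid, because the sentence also permits a sound one. The 4-df t test cannot be called valid whatever the ICC, because it depends on similar team sizes and similar between-CAC variance in the arms.

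This should be fixed: the omission is certain, its effect could be material, and it is cheap to close.

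**What to change.** State in the SAP that the primary effect for knowledge, skill use and member-rated team functioning is the TeamTRACS-minus-waitlist difference in change from baseline to 3 months, reported with a 95% CI that rests on the six CACs. Name one of two routes in advance:

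- the planned mixed model with a CAC-by-time random effect, small-sample df (about 4) and a pre-set rule for a zero variance estimate, for example individual-level df in that case; or
- a t test on the six CAC mean changes with 4 df, each CAC's change computed from all respondents at each wave so that turnover is covered.

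Disclose the limits of the chosen route, including the 4-df t test's sensitivity to unequal variances and team sizes. Treat within-arm change as descriptive and keep the planned team-level plots. Qualify the power sentence by test, effect size and ICC.

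The text costs a few lines and needs no new data. The real cost is lower stated power and wider intervals. At an assumed 0.5 SD, the CAC-mean test has 59% power at ICC 0 and 32% at 0.05, against 82% for the individual-level test at ICC 0. The half-width rises from 0.34 SD to between 0.48 and 0.89 SD.

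### Should the analysis by training attendance be replaced with a comparison of attendees against waitlist members?

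*Combined protocol and SAP*

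**What the plan says.** The Statistical Analysis Plan, under "Analyses of Effectiveness Outcomes", sets the order of the analyses: "Our primary analyses are intent-to-treat analyses including all participants in each condition". It then adds per-protocol "analyses testing for changes in knowledge and skill use by training attendance". That one sentence is the whole specification. It gives no comparator, model term or adjustment for who attends.

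Four other statements bear on it:

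- Randomization: "CACs randomized to the waitlist will receive the intervention after completing the follow-up survey". Nobody in a waitlist center can therefore be an attendee during the analysed period.
- Team Training Intervention: "The training will be delivered in a single session and be at least 4 hours". All members are invited and attendance is recorded.
- Team Training Intervention: "Team members are encouraged to identify specific goals for their team and make plans to use specific strategies from the training". Colleagues who did not attend may therefore share some of the benefit.
- Study Overview: "We expect team members to change during the study period and will include only current team members at each timepoint". The plan does not say how members who join after the session are classed for attendance.

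**The concern.** Attendance is a choice. If attendees are compared with non-attendees among those offered training, the contrast uses only the 4 TeamTRACS centers and gains nothing from randomisation. Engaged members probably attend more and may also improve more, and that difference would be read as a training effect. The comparator could also be contaminated in the other direction, because non-attendees work in a team that has just set goals and plans. Late joiners could be counted as non-attendees although they were never offered the session.

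At stake is a further test of knowledge and skill use, two of the three outcomes in the primary aims ("The primary aims of this pilot trial are to test the effects of TeamTRACS on knowledge, skill use, and team functioning"). It could come out positive when intent-to-treat does not. A comparison of attendees with waitlist members, by center, looks like an easy repair that needs only new wording.

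**Working it through.** **Inputs from the documents.** 4 TeamTRACS and 2 waitlist centers, with an estimated 25 members each. The stated total reproduces: 6 × 25 = 150, that is 100 against 50.

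**Assumptions, because the documents give no figures.** Attendance share p = 0.6-0.8; correlation of engagement with attendance 0.5; correlation of engagement with change r = 0.1-0.5; ICC of change 0-0.10; SD of change 1; full response unless stated.

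**Step 1, spurious difference with no training effect.** Against non-attendees, D = 0.5 × r × φ(k) / [p(1−p)], where k is the standard normal quantile at 1−p. Randomisation gives both arms the same expected change, so against the waitlist the difference is (1−p)D.

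| p | r | D, v non-attendees | (1−p)D, v waitlist |
|---|---|---|---|
| 0.6 | 0.1 | 0.080 | 0.032 |
| 0.6 | 0.2 | 0.161 | 0.064 |
| 0.6 | 0.3 | 0.241 | 0.097 |
| 0.6 | 0.5 | 0.402 | 0.161 |
| 0.8 | 0.1 | 0.087 | 0.017 |
| 0.8 | 0.2 | 0.175 | 0.035 |
| 0.8 | 0.3 | 0.262 | 0.052 |
| 0.8 | 0.5 | 0.437 | 0.087 |

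The waitlist contrast leaves 40% of the gap at p = 0.6 and 20% at p = 0.8.

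**Step 2, standard errors.** With n_a = 100p and n_n = 100(1−p):

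- Within centers: √[(1−ICC)(1/n_a + 1/n_n)]. At ICC 0.05 this is 0.199 (p = 0.6) and 0.244 (p = 0.8).
- Against waitlist: √[ICC(1/4 + 1/2) + (1−ICC)(1/n_a + 1/50)]. At ICC 0.05 this is 0.269 and 0.261; at ICC 0.10, 0.329 and 0.323. The test has 4 degrees of freedom and a critical t of 2.78.

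**Step 3, false positives with no effect.** In simulation over r = 0.2-0.5, ICC 0-0.10 and 60-100% response, the non-attendee test rejected in 8-54% of trials and the waitlist test in 4-8%. At r = 0.1 and full response, D divided by its standard error at ICC 0.05 is 0.080/0.199 = 0.40 (p = 0.6) or 0.087/0.244 = 0.36 (p = 0.8). That gives a rejection rate of about 7%; simulation gives about 5-7%.

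**Step 4, power of the replacement.** For a 0.5 SD difference at full response, power is 51-56% at ICC 0, 30-31% at ICC 0.05 and 22% at ICC 0.10. Its low false-positive rate therefore partly reflects a test that detects little.

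**Step 5, total error, √(bias² + SE²), p = 0.6.**

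| r | ICC | v non-attendees | v waitlist |
|---|---|---|---|
| 0.3 | 0.05 | √(0.241² + 0.199²) = 0.31 | √(0.097² + 0.269²) = 0.29 |
| 0.3 | 0.10 | √(0.241² + 0.194²) = 0.31 | √(0.097² + 0.329²) = 0.34 |
| 0.1 | 0.05 | √(0.080² + 0.199²) = 0.21 | √(0.032² + 0.269²) = 0.27 |

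The ranking turns on quantities nobody has. At p = 0.8 and r = 0.3 the waitlist contrast is ahead at both ICC values (0.27 against 0.36, and 0.33 against 0.35). Across the wider simulations with a 0.5 SD effect, it had the smaller error in 65 of 108 settings, but in only 9 of 36 at ICC 0.10. One reason is that benefit shared with non-attendees offsets selection in the within-center contrast. If half the effect reaches them, its expected value runs from 0.5 + 0.161 − 0.25 = 0.41 upward; with none shared it runs up to 0.5 + 0.437 = 0.94.

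**The case for a change.** The strongest case for a change does not depend on the assumed sizes. Whatever the selection, using the waitlist shrinks it to (1−p) of its size, and an unnamed comparator can be picked after the data are seen. At moderate to strong selection the inflation is large. The non-attendee test favoured training while intent-to-treat was not significant in 7-51% of simulated null trials. The data needed for the other contrast are already collected.

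The proportionality and the inflation both stand. Three things weaken the step from there to a required replacement. First, comparing those who received an intervention with the control arm is an ordinary meaning of per protocol, so the plan may already intend the proposed analysis. Second, the range starts at r = 0.2. The outcome is change from baseline, which removes stable differences between attendees and others, so weaker selection is plausible. Third, the intent-to-treat benchmark in the 7-51% figure was a t test on center means, whereas the plan names linear mixed models, so that figure describes the plan only loosely.

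The late-joiner point is a real gap in wording. If 10-30% of follow-up respondents were joiners counted as non-attendees, they would form 22-68% of that group. But those shares are assumed, and joiners have no pre-training survey from which to measure change. The plan also has staff report additions to each team, so joiners can be identified.

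**Conclusion.** No change to the plan is needed. What is established is narrow: an added analysis, below an explicit intent-to-treat primary, does not define its comparator or the class of members who join after the session. Analysts fill such a gap sensibly by stating the comparator, describing the result as exploratory and non-randomised at the person level, and showing late joiners apart.

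Replacing the analysis is a fair trade-off on which statisticians may differ. Under the assumptions above, it cuts the spurious difference from 0.16-0.44 SD to 0.04-0.16 SD for r = 0.2-0.5. The price is a 4 against 2 center comparison with about 22-31% power for 0.5 SD at ICC 0.05-0.10, and often larger total error at ICC 0.10. Dividing the intent-to-treat estimate by the share attending is no clean escape: it assumes that non-attendees gain nothing, which is doubtful in a team intervention.

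Every size here rests on attendance, selection and ICC values that the documents do not give. The main conclusion of the trial is the same whichever comparator is used.
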